8 SAFETY ASSESSMENTS

8.1 Adverse Events

An AE is defined as any untoward medical occurrence in a clinical investigation subject administered a pharmaceutical product, which does not necessarily have a causal relationship with this treatment. An AE can therefore be any unfavorable and/or unintended sign (including an abnormal laboratory finding), symptom, or disease temporally associated with the use of an investigational medicinal product, whether or not related to the investigational medicinal product. All AEs, including observed or volunteered problems, complaints, or symptoms, are to be recorded on the appropriate eCRF.

AEs, which include clinical laboratory test variables, will be monitored and documented from the time of informed consent until the Follow-Up Telephone Call. Patients should be instructed to report any AE that they experience to the Investigator, whether or not they think the event is due to study treatment. Beginning from the time of informed consent, Investigators should make an assessment for AEs at each visit and record the event on the appropriate AE eCRF.

Wherever possible, a specific disease or syndrome rather than individual associated signs and symptoms should be identified by the Investigator and recorded on the eCRF. However, if an observed or reported sign or symptom is not considered a component of a specific disease or syndrome by the Investigator, it should be recorded as a separate AE on the eCRF. Additionally, the condition that led to a medical or surgical procedure (e.g., surgery, endoscopy, tooth extraction, or transfusion) should be recorded as an AE, not the procedure itself.

Any medical condition already present at the Screening Visit should be recorded as medical history and not be reported as an AE unless the medical condition or signs or symptoms present at baseline changes in severity, frequency, or seriousness at any time during the study. In this case, it should be reported as an AE.

Clinically significant abnormal laboratory or other examination (e.g., ECG) findings that are detected during the study or are present at the Screening Visit and significantly worsen during the study should be reported as AEs, as described below. The Investigator will exercise his or her medical and scientific judgment in deciding whether an abnormal laboratory finding or other abnormal assessment is clinically significant. Clinically significant abnormal laboratory values occurring during the clinical study will be followed until repeat tests return to normal, stabilize, or are no longer clinically significant. Abnormal test results that are determined to be an error should not be reported as an AE. Laboratory abnormalities or other abnormal clinical findings (e.g., ECG abnormalities) should be reported as an AE if any of the following are applicable:

- If an intervention is required as a result of the abnormality;
- If action taken with the study drug is required as a result of the abnormality; or
- Based on the clinical judgment of the Investigator.

8.1.1 Adverse (Drug) Reaction

All noxious and unintended responses to a medicinal product related to any dose should be considered an adverse drug reaction. "Responses" to a medicinal product means that a causal relationship between a medicinal product and an adverse event is at least a reasonable possibility, i.e., the relationship cannot be ruled out.

8.1.2 Unexpected Adverse Drug Reaction

An Unexpected Adverse Drug Reaction is defined as an adverse reaction, the nature or severity of which is not consistent with the applicable product information.

8.1.3 Assessment of Adverse Events by the Investigator

The Investigator will assess the severity (intensity) of each AE as mild, moderate, or severe, and will also categorize each AE as to its potential relationship to study drug using the categories of yes or no.

Assessment of Severity

Mild – An event that is easily tolerated and generally not interfering with normal daily activities.

Moderate – An event that is sufficiently discomforting to interfere with normal daily activities.

Severe – An event that is incapacitating with inability to work or perform normal daily activities.

Causality Assessment

The relationship of an AE to the administration of the study drug is to be assessed according to the following definitions:

No (unrelated, not related, unlikely to be related) – The time course between the administration of study drug and the occurrence or worsening of the AE rules out a causal relationship and another cause (concomitant drugs, therapies, complications, etc.) is suspected.

Yes (possibly, probably, or definitely related) – The time course between the administration of study drug and the occurrence or worsening of the AE is consistent with a causal relationship and no other cause (concomitant drugs, therapies, complications, etc.) can be identified.

The definition implies a reasonable possibility of a causal relationship between the event and the study drug. This means that there are facts (evidence) or arguments to suggest a causal relationship.

The following factors should also be considered:

• The temporal sequence from study drug administration-

The event must occur after the study drug is given. The length of time from study drug exposure to the event should be evaluated in the clinical context of the event.

• Underlying, concomitant, intercurrent diseases-

Each report should be evaluated in the context of the natural history and course of the disease being treated and any other disease the patient may have.

• Concomitant drug-

The other drugs the patient is taking or the treatment the patient receives should be examined to determine whether any of them might be recognized to cause the event in question.

• Known response pattern for this class of study drug-

Clinical and/or preclinical data may indicate whether a particular response is likely to be a class effect.

· Exposure to physical and/or mental stresses-

The exposure to stress might induce adverse changes in the recipient and provide a logical and better explanation for the event.

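### The yes/no causality definitions in Protocol 8.1.3 leave out events with consistent timing and another identified cause, and conflict with the threshold in 8.1.1

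*Protocol*

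**What the plan says.** Protocol 8.1.3 has the investigator classify the relationship of each adverse event to study drug "using the categories of yes or no", and says that the definitions that follow govern the choice. Each category has a label and two conditions joined by *and*.

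- No is labelled "No (unrelated, not related, unlikely to be related". It applies where the time course "rules out a causal relationship and another cause (concomitant drugs, therapies, complications, etc.) is suspected".
- Yes is labelled "Yes (possibly, probably, or definitely related". It applies where the time course "is consistent with a causal relationship and no other cause (concomitant drugs, therapies, complications, etc.) can be identified".

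The text after the definitions speaks of a reasonable possibility and adds: "This means that there are facts (evidence) or arguments to suggest a causal relationship". A list of further factors follows: temporal sequence, other disease, concomitant drugs, class effects, and physical or mental stress, the last because it might "provide a logical and better explanation for the event".

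Section 8.1.1 sets the threshold for an adverse drug reaction in other terms. Its test reads: "a causal relationship between a medicinal product and an adverse event is at least a reasonable possibility, i.e., the relationship cannot be ruled out". It does not require that other causes be absent.

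**The concern.** A two-valued code works only if each event falls under one value. Here both definitions are conjunctions, and neither is the negation of the other. An investigator who finds that the timing fits the drug, and who also identifies another cause, has no code that the wording supports. A code is still needed, because Protocol 10.1.5 sends missing data back to the site as queries.

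The investigator must therefore set aside one of the conditions, and the protocol does not say which. Two investigators can code the same event differently in good faith. At stake is the consistency of every safety output that splits events by relationship, and whether related in the tables means the same as reaction in 8.1.1.

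**Working it through.** There is no stated figure to reproduce. The check applies the definitions as written and then traces where the code is used.

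**Step 1: the definitions as rules.** From 8.1.3:

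- Yes = timing consistent AND no other cause identified.
- No = timing rules causality out AND another cause at least suspected.

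For the pair to be exhaustive, No would have to be the negation of Yes: timing not consistent OR another cause identified. It is not.

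**Step 2: all combinations.**

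| Timing | Other cause | Code under 8.1.3 | Drug ruled out by timing (8.1.1)? |
|---|---|---|---|
| Rules out | None | Neither | Yes |
| Rules out | Suspected only | No | Yes |
| Rules out | Identified | No | Yes |
| Consistent | None | Yes | No |
| Consistent | Suspected only | Yes | No |
| Consistent | Identified | **Neither** | No |

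Of the 6 combinations, 2 give Yes, 2 give No and 2 give neither. These are combinations of conditions, not events, so 2 of 6 is not a rate. The first row is a gap in wording only, since any reader would code it No. The last row is the substantive gap.

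**Step 3: against 8.1.1.** In the last row, timing does not rule the drug out. Unless the other cause is strong enough to do so, the event is a reaction under 8.1.1 and yet fails Yes under 8.1.3.

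**Step 4: labels against definitions.** The Yes label extends to possibly related events, but its definition excludes any event with another identified cause. The No label extends to events unlikely to be related, but its definition demands timing that rules causality out. Each label is wider than its definition.

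**Step 5: where the code is used.**

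- Protocol 9.2.3 summarizes treatment-emergent events by relationship.
- The overview list in SAP 3.6.1 has 10 legible lines and 1 blank. Four use the code: treatment-emergent events by relationship, related treatment-emergent events, related treatment-emergent serious events, and related treatment-emergent events leading to study drug discontinuation. Each is repeated by system organ class and preferred term.
- SAP 3.6.1 counts a change in relationship as worsening. With a two-valued code that can only be a move from No to Yes, so the code can decide whether an event present before dosing becomes treatment-emergent.
- Protocol 8.3 requires serious events after the 30-day window to be reported if the investigator considers them related. It does not cite the 8.1.3 code, so this link is inferred.

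**The case against.** The strongest reply is that judgement already fills the gap. If identified means established as the actual cause, No is the natural code, just as it is for the first row of the table. If it means only a possible alternative, the word possibly, the reasonable-possibility sentence and the listed factors all lean towards Yes. This softens the point but does not remove it. The factors are to be considered in addition to the definitions, and none states which code applies when timing fits and another cause is found. The two readings in this reply also give opposite codes.

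A second objection is that the protocol does not define the difference between suspected and identified, so the edge of the gap is a matter of interpretation. That stands. A reader who treats any recognized alternative as identified would find a wider gap. On either reading a gap exists.

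Third, the adverse event summaries are descriptive, and all events are listed by patient, so individual cases can be reviewed again. The procedures for completing the eCRF, mentioned in Protocol 11.4, are not in the documents and may give sites further guidance. Both points limit the consequence. Neither corrects the definition.

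A reader might also take the creatine kinase note in Protocol 4.6 as a ready example, because it asks sites about potential causes. It is a poor one: the criterion covers only unexplained elevations, so an elevation with an established cause arguably falls outside it.

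**Conclusion.** The point stands as an error in a stated rule. The definitions in 8.1.3 do not cover an event with consistent timing and another identified cause, and they conflict with 8.1.1 and with their own labels. The by-relationship summaries, 4 of the 10 legible overview lines and the worsening rule depend on the code; late serious-event reporting may. The number of events involved cannot be estimated. The conclusion assumes that the two definitions mean what they say and that no unseen site instruction overrides them.

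Three stronger inferences are not supported:

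- *Expedited and complaint reporting are compromised.* Protocol 8.5 and 8.6 turn on the adverse reaction term, which 8.1.1 defines broadly, and not on the 8.1.3 code.
- *The open-label design biases the comparison between arms.* Every arm receives pemafibrate, and nothing in the documents gives a direction in which coding would differ.
- *The wording sends possible reactions to No.* Read literally, such events meet neither category. The demonstrable result is inconsistency.

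Efficacy, serious-event reporting up to 30 days (which is regardless of causality), the laboratory shift tables and the Hy's Law outputs are not shown to be affected. Counts of all treatment-emergent events can change only through the worsening rule.

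**What to change.** Reconcile 8.1.3 with 8.1.1 so that the two categories cover every event:

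- **Yes:** a reasonable possibility of a causal relationship (it cannot be ruled out), even if another possible cause exists. This removes the condition on other causes.
- **No:** no reasonable possibility of a causal relationship.
- State that the unlikely wording in the No label applies only where there is no reasonable possibility.
- Keep the listed factors as aids to this judgement, and carry the wording into the eCRF instructions.

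The threshold is the protocol's own, from 8.1.1. The drafting is small, but the change is a protocol amendment with the review and approval described in Protocol 12.1, including the IRB. SAP 2.3.1 refers to patients who consented under protocol version 1.0, so some events may already be coded. These need a check or re-review so that one rule applies throughout. Somewhat more events will be coded as related.

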8.2 Serious Adverse Events

An AE or adverse reaction is considered serious if, in the view of either the Investigator or Sponsor, it results in any of the following outcomes:

- Death;
- A life-threatening AE;

Note: An AE or adverse reaction is considered "life-threatening" if, in view of either the Investigator or Sponsor, its occurrence places the patient at immediate risk of death. It does not include an event that, had it occurred in a more severe form, might have caused death;

• Requires hospitalization or prolongation of existing hospitalizations;

Note: Any hospital admission with at least one overnight stay will be considered an inpatient hospitalization. An emergency room or urgent care visit without hospital admission will not be recorded as an SAE under this criterion, nor will hospitalization for a procedure scheduled or planned before signing of informed consent, or elective treatment of a pre-existing condition that did not worsen from Baseline. However, unexpected complications and/or prolongation of hospitalization that occur during elective surgery should be recorded as AEs and assessed for seriousness. Admission to the hospital for social or situational reasons (i.e., no place to stay, live too far away to come for hospital visits, respite care) will not be considered inpatient hospitalizations;

- A persistent or significant disability/incapacity or substantial disruption of the ability to conduct normal life functions;
- A congenital anomaly/birth defect; and/or
- An important medical event;

Note: Important medical events that do not meet any of the above criteria may be considered an SAE when, based upon appropriate medical judgment, they may jeopardize the patient and may require medical or surgical intervention to prevent one of the outcomes listed above. Examples of such medical events include allergic bronchospasm requiring intensive treatment in an emergency room or at home, blood dyscrasias or convulsions that do not result in inpatient hospitalizations, or the development of drug dependency.

8.3 Serious Adverse Event Reporting – Procedures for Investigators

Initial Reports

All SAEs occurring from the time of informed consent until 30 days following the last administration of study drug must be reported to within 24 hours of the

knowledge of the occurrence. After the 30-day reporting window, any SAE that the Investigator considers related to study drug must be reported to the sponsor/designee.

To report the SAE, complete the SAE form electronically in the electronic data capture (EDC) system for the study. When the form is completed, personnel will be notified electronically by the EDC system and will retrieve the form. If the event meets serious criteria and it is not possible to access the EDC system, send an email to state at [contact] or call the state SAE reporting line (phone number listed below), and fax/email the completed paper SAE form to system becomes available, the SAE information must be entered as soon as possible of the system becoming available.

Follow-Up Reports

The Investigator must continue to follow the patient until the SAE has subsided or until the condition becomes chronic in nature, stabilizes (in the case of persistent impairment), or the patient dies.

Within 24 hours of receipt of follow-up information, the Investigator must update the SAE form electronically in the EDC system for the study and submit any supporting documentation (e.g., patient discharge summary or autopsy reports) to the procedures outlined above for initial reporting of SAEs.

8.4 **Pregnancy Reporting**

If a patient becomes pregnant from the time of initiation of study drug through the safety follow-up period defined in the protocol, the Investigator is to stop dosing with study drug immediately and the patient should be withdrawn from the study. ET procedures should be implemented at that time.

A pregnancy is not considered to be an AE or SAE; however, it must be reported to will then within 24 hours of knowledge of the event. Will then will then provide the Investigator/site the Exposure In Utero (EIU) form for completion. The Investigator/site must complete the EIU form and fax/email it back to within 24 hours of completion.

If the female partner of a male patient becomes pregnant while the patient is receiving study drug or within the safety follow-up period defined in the protocol, the Investigator should notify as described above.

The pregnancy should be followed until the outcome of the pregnancy, whenever possible. Once the outcome of the pregnancy is known, the EIU form should be completed and faxed/emailed to

If the outcome of the pregnancy meets the criteria for immediate classification as an SAE (i.e., postpartum complication, spontaneous abortion, stillbirth, neonatal death, or congenital anomaly), the Investigator should follow the procedures for reporting an SAE.

8.5 Expedited Reporting

The Sponsor/designee will report all relevant information about Suspected Unexpected Serious Adverse Reactions (SUSARs) that are fatal or life-threatening as soon as possible to the Food and Drug Administration (FDA) and in any case no later than 7 days after knowledge by the Sponsor/designee of such a case. Relevant follow-up information will subsequently be communicated within an additional 8 days.

All other SUSARs will be reported to the FDA as soon as possible but within a maximum of 15 days of first knowledge by the Sponsor/designee.

The Sponsor/designee will also inform all Investigators as required per local regulation.

The requirements above refer to the requirements relating to investigational medicinal product.

8.6 Special Situation Reports

Special situation reports include reports of overdose, misuse, abuse, medication error, and reports of adverse reactions associated with product complaints.

- **Overdose:** Refers to the administration of a quantity of a medicinal product given per administration or cumulatively (accidentally or intentionally), which is above the maximum recommended dose according to the protocol. Clinical judgement should always be applied. In cases of a discrepancy in the drug accountability, overdose will be established only when it is clear that the patient has taken additional dose(s) or the Investigator has reason to suspect that the patient has taken additional dose(s).
- **Misuse:** Refers to situations where the medicinal product is intentionally and inappropriately used in a way that is not in accordance with the protocol instructions or local prescribing information and may be accompanied by harmful physical and/or psychological effects.
- Abuse: Is defined as persistent or sporadic, intentional excessive use of a medicinal product, which is accompanied by harmful physical or psychological effects.
- **Medication error:** Is any unintentional error in the prescribing, dispensing, or administration of a medicinal product by a healthcare professional, patient, or consumer, respectively. The administration or consumption of the unassigned treatment and administration of an expired product are always reportable as medication errors, cases of patients missing doses of investigational product are not considered reportable as medication errors.
- **Product complaint:** Is defined as any written, electronic, or oral communication that alleges deficiencies related to the identity, quality, durability, reliability, safety, effectiveness, or performance of a drug or device after it is released for distribution. A special situations form will only be completed if a complaint is associated with an adverse drug reaction.

All special situation events as described above must be reported on the Special Situations Report form and faxed/emailed to for the second (contact information listed below) within 24 hours of knowledge of the event. All AEs associated with these Special Situation reports should be reported as AEs or SAEs as well as recorded on the AE eCRF and/or the SAE report form. Details of the symptoms and signs, clinical management, and outcome should be provided, when available.

8.7 Clinical Laboratory Evaluations

Clinical laboratory tests will be conducted according to the Schedule of Procedures in Appendix A. See Appendix B for a complete list of laboratory analytes.

8.8 Vital Signs

Vital signs, systolic and diastolic BP, pulse, respiratory rate, and body temperature will be measured (sitting) after resting for a minimum of 5 minutes at the times indicated in the Schedule of Procedures in Appendix A. Patients should avoid smoking, caffeine, or exercise within 30 minutes prior to BP measurement. On Days 1, 14, and 28, BP and pulse must be measured prior to administration of study drug and again approximately 1 hour post-administration.

Additional measurements of vital signs may be performed at the discretion of the Investigator.

8.9 Electrocardiograms

For each patient, a 12-lead digital ECG will be collected locally according to the Schedule of Procedures in Appendix A. Patients must be supine for approximately 5 to 10 minutes before ECG collection and remain supine but awake during ECG collection.

ECGs will be interpreted locally by a qualified physician as soon after the time of ECG collection as possible and, ideally, while the patient is still present, to determine whether the patient meets entry criteria and for immediate patient management, should any clinically relevant findings be identified. The qualified physician must document his/her review of the ECG at the time of evaluation.

The ECGs will be maintained at the site and made available to the Sponsor as requested.

